6.5.2.1 Liver Safety Assessment

The liver safety assessments will be summarized by the categories below based on the measurements from Alkaline Phosphatase (ALP), Alanine Transaminase (ALT), total bilirubin, Aspartate Transaminase (AST) and their combination. These parameters will be based on measurements from a central laboratory.

The subject's highest value during the entire active-dose study period (from day of first dose of fezolinetant until last dose of extension treatment period + 1 day) will be used.

- ALT > 3xULN, > 5xULN, > 8xULN, > 10xULN, > 20xULN
- AST > 3xULN, > 5xULN, > 8xULN, > 10xULN, > 20xULN
- ALT or AST > 3xULN, > 5xULN, > 8xULN, > 10xULN, > 20xULN
- ALP > 1.5 xULN
- Total Bilirubin > 2xULN
- (ALT or AST > 3xULN) and Total Bilirubin > 2xULN
- (ALT or AST > 3xULN) and ALP < 2xULN and Total Bilirubin > 2xULN

The last 2 criteria where 2 or more parameters are evaluated will be with the measurements on the same day or up to 1 day apart. The denominator for each criterion will be the number of subjects who have at least one value during the active-dose study period. The number and percentage of subjects meeting the criteria during the active-dose study period will be summarized by treatment group.

Due to the COVID-19 pandemic, subjects might not have been able to visit the clinical site and have clinical laboratory tests taken at the clinical site and evaluated by the central laboratory, in this case clinical laboratory tests were performed taken by a local laboratory. The liver biochemistry safety assessments will be summarized including central and locally collected laboratory data due to the COVID-19 pandemic. This analysis is considered the primary analysis for the liver safety assessment.

As a secondary analysis for liver biochemistry, the analysis will be repeated with the data evaluated by the central laboratory but excluding the data that are impacted by COVID-19 pandemic, which include the data recorded after the subjects were diagnosed of COVID-19, after study drug discontinuation due to COVID-19, during dose interruption due to COVID-19, and visits that are out of protocol windows or data collected via home visits due to COVID-19 recorded in the eCRF.

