- s. While scheduled for week 4 (visit 3), PGx sample can be taken at any time during the study after signed informed consent and enrollment into the study.
- t. The VMS diary will be kept by subjects. Subjects will record the VMS frequency and severity of each VMS in the ePRO diary on a daily basis from the screening visit (days -35 to -1 [visit 1]) through the follow-up visit (week 55 [visit 16]). Night sweats should be recorded no later than in the morning upon awakening to start a new day.
- u. Includes BSAP, P1NP and CTX.
- v. Subjects will be assigned study drug as a kit in blister packaging. The first intake of study drug will take place at the study site on day 1 (visit 2) under the supervision of the study staff. On study visit days, the daily dose of study drug will be taken at the study site, under the supervision of the study staff, after collection of predose blood samples. On all other days throughout the treatment period, subjects will be instructed to take their dose of study drug at home, in the morning with water.
- w. Subjects will be asked to return all unused study drug. Compliance of study drug intake will be assessed by counting returned study drug and recorded in the source documents and the interactive response technology.
- x. AEs and intake of concomitant medication(s) will be monitored continuously from informed consent until the last study-related activity.
- y. Screening (visit 1), Randomization, week 0 (visit 2) and EOT/ED week 52 (visit 15) visits must be conducted in the clinic and not with home healthcare, telemedicine conferences or local laboratory.

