5 TREATMENTS AND EVALUATION

5.1 Dosing and Administration of Study Drug(s) and Other Medication(s)

5.1.1 Dose/Dose Regimen and Administration Period

Subjects will be screened up to 35 days prior to randomization. Informed consent/ authorization will be obtained prior to randomization and before any study-related procedures are performed.

Subjects will be assigned study drug as a kit at visits indicated in the Schedule of Assessments [Table 1]. Each kit will contain blister wallets containing either fezolinetant or placebo. Study drug intake will be done with a glass of water. The first intake of study drug will take place at the study site on day 1 (visit 2) under the supervision of the study staff.

On study visit days study drug will be taken at the study site, under the supervision of the study staff, after collection of predose blood samples. On all other days throughout the treatment period, subjects will be instructed to take their dose of study drug at home, in the morning with water.

In the case of a missed dose, the subject should skip the missed dose and continue with the next scheduled dose.

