6.5 Analysis of Safety

All analysis of safety will be presented by the four treatment groups, as described in Section 6.1 (General Considerations), for SAF_F, unless specified otherwise. For analyses by visit, the visit windows from Section 6.10.1.2 will be applied, and they are all defined relative to the start of fezolinetant. Except for adverse events and follow-up visit data, only data up to one day after the last dose date will be considered for the analyses.

The baseline value for safety endpoint will be the last non-missing value taken on or prior to first dose of fezolinetant unless otherwise noted.

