6.10.1 Analysis Windows

Study Day for analysis windows during the double-blind treatment phase will be calculated as date of visit/assessment – first dose date +1.

Study Day during the extension phase will be calculated as date of visit/assessment – first dose date of the extension phase +1.

Study Day for the follow-up (FUD) phase will be calculated as date of visit/assessment – last dose date of study treatment (Date of EOT).

Fezolinetant Study Day (FD) will be calculated as date of visit/assessment – first dose date of fezolinetant +1. Note that this is the same as Study Day for subjects randomized to fezolinetant in the double-blind treatment phase. Post-baseline data prior to first dose of fezolinetant Day 1 is excluded from the analyses described in this SAP unless otherwise noted.

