6.10 Additional Conventions

6.10.1 Analysis Windows

Study Day for analysis windows during the double-blind treatment phase will be calculated as date of visit/assessment – first dose date +1.

Study Day for the follow-up phase will be calculated as date of visit/assessment – last dose date of double-blind treatment.

As noted in Section 1 only data pertaining to the double-blind treatment phase will be used in the 12-week treatment phase analysis:

- The active treatment extension period data (beginning from the second day of the active treatment extension period) will be excluded, assuming the Week 12 assessments are done before the first dose of active treatment extension period.
- Follow-up data that also falls into the active treatment extension period will be excluded (i.e., early discontinuations within the active treatment extension period phase).

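### The 52-week SAP's liver peak-value window opens on the day of the first fezolinetant dose, so a predose Week 12 sample that the SAP elsewhere makes the baseline can count as an on-fezolinetant result

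*SAP*

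**What the plan says.** For the categorical liver table, 52-week SAP 6.5.2.1 uses each woman's "highest value during the entire active-dose study period (from day of first dose of fezolinetant"; in full, the window runs "from day of first dose of fezolinetant until last dose of extension treatment period + 1 day". The denominator of each criterion is "the number of subjects who have at least one value during the active-dose study period". Section 6.10.1 computes fezolinetant day (FD) as assessment date minus "first dose date of fezolinetant +1". No clock time enters the formula.

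Other parts of the same SAP treat a sample taken before the first dose on that date as baseline:

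- Section 6.5: the safety baseline "will be the last non-missing value taken on or prior to first dose of fezolinetant".
- Section 5, baseline table: liver safety assessments are listed by name, with the Week 12 baseline for placebo/fezolinetant women. The text below the table says that 52-week endpoints run from the first dose of fezolinetant, not from the day of that dose.
- Section 6.10.1.2: for liver biochemistry, baseline runs through FD1 and the first post-baseline window is FD2 to FD22.

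The order of events comes from the protocol. Table 1 schedules clinical laboratory tests and drug dispensing at Visit 5 (Day 85). Section 5.1.1 says that on visit days "study drug will be taken at the study site, under the supervision of the study staff, after collection of predose blood samples". The 12-week SAP, section 6.10.1, proceeds on the same footing, "assuming the Week 12 assessments are done before the first dose of active treatment extension period".

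**The concern.** A liver sample taken after 12 weeks of placebo, before any fezolinetant, says nothing about fezolinetant. If it enters the peak-value table it can cause two errors.

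- **Numerator.** An elevation that arose on placebo can be reported under placebo to 30 mg or placebo to 45 mg. The 12-week analysis can report the same value under placebo.
- **Denominator.** A woman whose only value in the window is the predose one counts as evaluated on fezolinetant. This lowers the reported rate.

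The protocol classes liver injury as an important potential risk (section 1.5), and its modelling predicted no transaminase elevation above 3 times the upper limit of normal (ULN) at 30 or 45 mg once daily (section 2.2.2). Against that expectation even one spurious case would be noticed, and the 52-week table has no concurrent placebo column beside it.

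**Working it through.** **1. Where the sample falls.** FD = draw date − first fezolinetant dose date + 1.

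| Draw | FD | Window from FD1 (6.5.2.1) | Window from FD2 |
|---|---|---|---|
| Same date as first fezolinetant dose | 0 + 1 = 1 | in | out |
| One day earlier | −1 + 1 = 0 | out | out |

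The rule therefore captures the sample only when draw and first fezolinetant dose share a date. Table 1 and protocol section 5.1.1 make that the scheduled case.

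**2. Whether another rule removes it.**

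- The FD2 start in 6.10.1.2 does not reach the peak table, because section 6.5 applies those windows to by-visit analyses.
- The exclusion in 6.10.1 concerns post-baseline data before fezolinetant Day 1. This sample is a baseline value dated Day 1, so the exclusion does not clearly apply.
- The section 5 statement that endpoints run from the first dose points towards exclusion, but 6.5.2.1 is the more specific text and says day.

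No sentence says that the baseline sample is left out of the peak table.

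**3. Its status in the 12-week SAP.** Section 6.10.1 drops extension data only from the second extension day. Section 6.10.1.2 gives the Week 12 liver window as Days 72 to 92, which contains Day 85. The sample stays in as a placebo result.

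**4. Number of women.** The plan's own inflation reproduces: 120 / (1 − 0.20) = 150 per arm. Conversely, 150 × 0.80 = 120 placebo completers could switch. The re-randomization ratio is not stated. Assuming an even split, 120 / 2 = 60 per dose.

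**5. Weight of one case.** 1/60 = 1.7 percentage points in a switched group.

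**6. Expected count.** The documents give no rate of ALT or AST above 3 × ULN on placebo at this draw, so p below is assumed.

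| Assumed p | Expected = 120 × p | Chance of at least one = 1 − (1 − p)^120 |
|---|---|---|
| 0.5% | 0.6 | 45% |
| 1% | 1.2 | 70% |
| 2% | 2.4 | 91% |

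These figures count women elevated at the draw, not women falsely added to the table. A woman whose elevation persists at a later on-drug sample is counted under either window. Both columns are therefore upper figures.

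**7. Nearest evidence in the documents.** Phase 2b had nine women above 3 × ULN. Seven received 120 mg or more per day and two received 60 mg per day (protocol section 2.2.2). Since 7 + 2 = 9, none was among the 44 randomized to placebo (Table 2). With 0 of 44, the one-sided 95% upper bound is 1 − 0.05^(1/44) = 6.6%, so the assumed range is neither confirmed nor excluded.

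**The case against.** The best defence is that the SAP's intention is plain. Section 5 names liver safety assessments, gives switched women the Week 12 baseline and starts endpoints at the first dose, so a programmer who reads the whole document would leave the sample out. That shows what was probably meant. It does not remove the conflict, because the only sentence that defines the peak window says day of first dose. A reader might infer that the SAP settles the sample as a fezolinetant result. It does not: it gives two incompatible answers.

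A reader might also infer that every switched woman is affected. The documents do not support that. Week 12 laboratory tests may be missing, or done locally or by home healthcare under the COVID-19 provisions, and so fall on an earlier date. Protocol footnotes use the word predose for pharmacokinetic and pharmacodynamic samples. The safety panel is not itself labelled predose, and the 12-week SAP only assumes the order.

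The defence is also right about size. Protocol Appendix 12.4 requires repeat testing within 72 hours of notification of a value above 3 × ULN, and Visit 5b (Week 14) includes liver biochemistry. An elevation still present at those samples in a woman now on fezolinetant counts whichever window is used.

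Other points reduce the harm. The 52-week summaries are descriptive. The switched women form separate groups, listings include baseline data, and the biochemistry shift tables start from the Week 12 baseline, so a careful reader could trace a spurious case. These points limit the consequence, but they do not make the table correct.

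**Conclusion.** The point stands as an internal contradiction in the 52-week SAP. Followed literally, 6.5.2.1 lets a placebo-period value supply a switched woman's on-fezolinetant peak and place her in the denominator, while sections 5, 6.5 and 6.10.1.2 make that value the baseline. It applies when draw and first fezolinetant dose share a date, with the draw first.

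The size is modest. One misattributed case adds about 1.7 percentage points to a switched group of about 60, given the planned 20% dropout and an even split. The 0.6 to 2.4 expected cases rest on assumed rates and are upper figures. It would be tempting to quote a 45% to 91% chance of at least one false case. The documents do not support that as a forecast, since the rates are assumed and persistent elevations would count anyway.

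The Day 1 sample of women first randomized to fezolinetant is also FD1. For the transaminase categories the effect there should be small, because exclusion criterion 11 admits ALT or AST only up to 1.5 × ULN. The error therefore bears mainly on the two switched groups. No primary or key secondary result depends on it.

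**What to change.** In 52-week SAP 6.5.2.1, define the window as samples taken after the first fezolinetant dose: from FD2, as the by-visit table already does, or by sample time after the dose on Day 1. State that the sample used as baseline counts in neither the numerator nor the denominator.

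Start the liver window in 12-week SAP 6.5.2.1 the same way, after the first dose of study drug. The closing point in that sentence should be corrected at the same time, since as written it ends at the first dose of the double-blind period.

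The cost is about one phrase in each SAP and a matching change in the table program. No new data are needed.

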| VMS | Vasomotor Symptoms |
| WPAI | Work Productivity and Activity Impairment |

List of Key Terms

| Terms | Definition of terms | |
|----------------------------------|---|--|
| Double-blind Treatment Period | The 12 weeks of treatment after the first administration of study drug and prior to first administration of study drug in the extension period. Only this period contains a placebo treatment. | |
| Extension Treatment Period | Period of time after the first administration of study drug in the extension period after completing 12 weeks of placebo-controlled double-blind treatment until the last dose of the study drug (at Week-52 or early discontinuation). | |
| Follow-up Period | Period of time after the last dose of study drug or last assessment of the protocol. Additional safety data and follow-up observations for sustained adverse events are conducted during this period. | |

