I. LIST OF ABBREVIATIONS AND KEY TERMS

List of Abbreviations

| Abbreviations | Description of abbreviations |
|---------------|-------------------------------------|
| ANCOVA | Analysis of Covariance |
| ASCM | Analysis Set Classification Meeting |
| ATE | Active Treatment Extension |
| CI | Confidence Intervals |
| СМН | Cochran Mantel Haenszel |
| COVID-19 | Coronavirus Disease 2019 |
| FAS | Full Analysis Set |
| GCP | Good Clinical Practice |
| ISE | Integrated Summary of Efficacy |
| MAR | Missing at Random |
| MMRM | Mixed Model Repeated Measures |
| PAP | Psychometric Analysis Plan |
| PKAS | Pharmacokinetics Analysis Set |
| PPS | Per-Protocol Analysis Set |
| SAF | Safety Analysis Set |
| SAP | Statistical Analysis Plan |
| SD | Standard Deviation |
| TLF | Tables, Listings and Figures |
| VMS | Vasomotor Symptoms |

List of Key Terms

| Terms | Definition of terms |
|--------------------------------------|--|
| Double-blind Treatment Period | The 12 weeks of treatment after the first administration of study drug and prior to first administration of study drug in the active treatment extension period. Only this period contains a placebo treatment. |
| Active Treatment Extension Period | Period of time after the first administration of study drug in the active treatment extension period after completing 12 weeks of placebo- controlled double-blind treatment until the last dose of the study drug (at Week 52 or early discontinuation). |
| Follow-up Period | Period of time after the last dose of study drug or last assessment of the protocol. Additional safety data and follow-up observations for sustained adverse events are conducted during this period. |

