6.5.2.1 Liver Safety Assessment

The liver safety assessments will be summarized by the categories below based on the measurements from Alkaline Phosphatase (ALP), Alanine Transaminase (ALT), total bilirubin, Aspartate Transaminase (AST) and their combination. These parameters will be based on measurements from a central laboratory.

The subject's highest value during the double-blind investigational period (from day of first dose of study drug until first dose of double-blind treatment period) will be used.

- ALT > 3xULN, > 5xULN, > 8xULN, > 10xULN, >20xULN
- AST > 3xULN, > 5xULN, > 8xULN, > 10xULN, > 20xULN
- ALT or AST > 3xULN, > 5xULN, > 8xULN, > 10xULN, >20xULN
- ALP > 1.5 xULN
- Total Bilirubin >2xULN
- (ALT or AST > 3xULN) and Total Bilirubin > 2xULN
- (ALT or AST > 3xULN) and ALP< 2xULN and Total Bilirubin > 2xULN

The last 2 criteria where 2 or more parameters are evaluated will be with the measurements on the same day or up to 1 day apart. The denominator for each criterion will be the number of subjects who have at least one value during the double-blind period. The number and percentage of subjects meeting the criteria during the double-blind period will be summarized by treatment group.

Due to COVID-19, patients might not be able to visit the clinical site and have clinical laboratory tests taken at the clinical site and evaluated by the central laboratory, in this case clinical laboratory tests can be taken by a local laboratory. The liver biochemistry safety assessments will be summarized including central and locally collected laboratory data due to COVID-19. This analysis is considered the primary analysis for the liver safety assessments.

The secondary analysis for liver biochemistry will be repeated by the data evaluated by the central laboratory but excluding the data that are impacted by COVID-19, which include the data recorded after the subjects were diagnosed of COVID-19, after study drug discontinuation due to COVID-19, during dose interruption due to COVID-19, and visits that are out of protocol window or data collected via home visits due to COVID-19 recorded in the eCRF.

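### The liver-maximum windows in both SAPs open on the calendar day of first dose, so they admit the pre-dose baseline draw, which for placebo women at Week 12 was taken on placebo; the 12-week window end is also a drafting slip

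*SAP*

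**What the plan says.** **The threshold tables.** In the 52-week SAP, Section 6.5.2.1, every ALT, AST, ALP and bilirubin row uses the "highest value during the entire active-dose study period (from day of first dose of fezolinetant until last dose of extension treatment period", plus one day. On the denominator it says: "The denominator for each criterion will be the number of subjects who have at least one value during the active-dose study period". In the 12-week SAP, Section 6.5.2.1, the window runs "from day of first dose of study drug until first dose of double-blind treatment period". Neither section limits the maximum to post-baseline values.

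**The baseline.** The baseline table in Section 5 of the 52-week SAP has a row that names the liver safety assessments. It sets baseline at randomization for women on fezolinetant throughout and at the start of the extension (Week 12) for placebo/fezolinetant women. Section 6.5 of each SAP takes as baseline the last value up to and including the first dose (of fezolinetant in the 52-week SAP, of study drug in the 12-week SAP). The by-visit tables in Section 6.10.1.2 of both SAPs place day 1 in the baseline row and open the first post-baseline liver window on day 2.

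**Order of draw and dose.** Under Protocol Section 5.1.1, drug on visit days is taken at the site once the pre-dose blood has been collected, and the first dose is given at Visit 2.

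**Which period owns the Week 12 draw.** The Key Terms in the 52-week SAP define the extension as the "Period of time after the first administration of study drug in the extension period", and the double-blind period as "The 12 weeks of treatment after the first administration of study drug and prior to first administration of study drug" of the extension. Section 6.10.1 of the 12-week SAP says "The active treatment extension period data (beginning from the second day of the active treatment extension period) will be excluded". The cut from the second day rests on a premise that the same sentence gives, namely "assuming the Week 12 assessments are done before the first dose of active treatment extension period". Section 6.10.1 of the 52-week SAP says: "Post-baseline data prior to first dose of fezolinetant Day 1 is excluded from the analyses described in this SAP unless otherwise noted".

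**The concern.** A value cannot sensibly be both the baseline and an on-treatment maximum, yet the stated window lets one draw be both. At randomization this matters little. At Week 12 in the placebo arm it matters more, because that draw follows 12 weeks of placebo and the 52-week table shows these women only in fezolinetant columns. A transaminase, ALP or bilirubin elevation that arose on placebo could be reported as a fezolinetant elevation. A woman with no liver value after her first fezolinetant dose would also count as tested.

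Protocol Section 1.5 names liver injury as an important potential risk, and Section 6.5.2.1 is where threshold crossings are counted. The 12-week version is the only placebo-controlled one, so a window that opens and closes on the same event needs correcting before it is programmed.

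**Working it through.** The documents give no figure to reproduce here. The check compares the window limits with the order of draw and dose, then bounds the size.

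**1. Where the pre-dose draw falls.** Section 6.10.1 of the 52-week SAP defines fezolinetant day as assessment date minus first fezolinetant dose date, plus 1. If draw and first dose share a date, the draw is on day 0 + 1 = 1. The liver maximum starts on the day of first dose, so the draw is in. The by-visit liver windows start on day 2, so there it is baseline only.

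**2. Scheduled liver draws** (Protocol Table 1; Visits 2b and 5b include liver biochemistry):

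| Window | Visits counted | Total | Pre-dose | From day 2 |
|---|---|---|---|---|
| 52-week, fezolinetant throughout | 2, 2b, 3, 4, 5, 5b (6) + 6 to 14 (9) + 15 (1) | 16 | 1 (Visit 2) | 15 |
| 52-week, placebo/fezolinetant | 5, 5b (2) + 6 to 14 (9) + 15 (1) | 12 | 1 (Visit 5, on placebo) | 11 |
| 12-week, whole period | 2, 2b, 3, 4, 5 | 5 | 1 (Visit 2) | 4 |

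Read literally, the 12-week window holds only the Visit 2 draw: 1 of 5, and 0 of the 4 draws that follow the first dose.

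**3. Whether the Week 12 draw is a placebo value.** The Key Terms start the extension after its first administration, and the 12-week SAP assumes that Week 12 assessments come first. By both SAPs' definitions the draw belongs to the double-blind period. It enters the 52-week window only if the first extension dose is taken on the same date. Table 1 dispenses drug at Week 12 and the dose is taken on site after the blood draw, so this is the expected case. If the first dose is a day later, the draw falls outside.

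**4. Size of one case.**
- Placebo women entering the extension: 150 × 0.8 = 120, up to 150 with no loss. The 20% is the planning assumption for dropout before Week 12.
- Per dose, assuming an equal split (no ratio is stated): 120/2 = 60 to 150/2 = 75.
- One misattributed woman: 1/60 = 1.67% to 1/75 = 1.33% of her column.

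**5. How many cases.** The documents give no rate of ALT or AST above 3×ULN at a single placebo draw. With 120 women and assumed rates of 0.1%, 0.25%, 0.5% and 1%, the expected number is 120 × rate = 0.12, 0.30, 0.60 and 1.20. The chance of at least one, 1 − (1 − rate)^120, is 11%, 26%, 45% and 70%. These are illustrations, not estimates.

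**6. Denominator.** Counting women who have no post-dose value pulls the percentage down. For illustration, 3 cases in an arm of 150 give 3/150 = 2.00%. If 15 of the 150 had no post-dose value, the correct figure would be 3/135 = 2.22%.

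**The case against.** The strongest reply is that the intent is already clear. Section 5 of the 52-week SAP gives the liver assessments a Week 12 baseline in placebo/fezolinetant women and says that safety changes are judged from exposure to fezolinetant onward. A careful programmer could conclude that the Week 12 draw is baseline and leave it out. This stands as evidence of intent, and it rules out reading the window as a deliberate choice to count baseline values as on-treatment. It does not remove the conflict, because 6.5.2.1 states its own window without a post-baseline limit. The general exclusion, "Post-baseline data prior to first dose of fezolinetant Day 1 is excluded from the analyses described in this SAP unless otherwise noted", does not settle it either: it can be read as dropping everything before the dose, or only data before Day 1.

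The 12-week window end is an obvious slip. Its own paragraph speaks of the double-blind period, and Sections 6.5 and 6.10.1.2 of that SAP set the cut-off at one day after the last dose. A reader might infer that the 12-week table would contain no post-dose data. Nobody is likely to program it that way, and the documents do not support that forecast.

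A reader might also infer that the Week 12 draw would be counted in both liver tables. That needs the 12-week window end to be corrected first; under the literal wording the draw is not in the 12-week table at all.

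On likelihood, the phase 2b study had nine subjects above 3×ULN: seven at 120 mg or more a day and two at 60 mg, so 9 − 7 − 2 = 0 among the 44 randomized to placebo (Protocol Sections 1.3.2 and 2.2.2). Protocol Section 1.5 does report mild transaminase elevations on placebo in earlier studies, but none stated to exceed 3×ULN. This makes a false count less likely without excluding it: with a true rate of 1%, zero in 44 would occur with probability 0.99^44 = 0.64. At randomization a false transaminase count is unlikely, since entry caps ALT and AST at 1.5×ULN. Those caps do not limit the Week 12 draw.

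**Conclusion.** The point holds as an internal conflict that should be corrected. Followed literally, 6.5.2.1 of the 52-week SAP places a placebo-exposed Week 12 draw in a fezolinetant column, and 6.5.2.1 of the 12-week SAP ends its window where it begins.

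The consequence is limited. Only descriptive liver tables are affected; the co-primary tests, alpha, power and sample size are not. The number of women affected cannot be derived and is probably small. A misattributed value would add to the fezolinetant count rather than hide a case, and it would appear only in the separate placebo/30 mg and placebo/45 mg columns. The denominator effect runs the other way and needs women with no post-dose liver value. The sizes shown assume 0% to 20% loss before the extension, an equal split, and draw and first extension dose on the same date.

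A reader might go further and infer that the bilirubin row is distorted because Gilbert's syndrome is eligible without a numeric cap on total bilirubin. That is not a window problem: a persistent elevation is counted whichever day the window opens, so it gives no ground for splitting that row.

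**What to change.** - **Both SAPs, 6.5.2.1:** use only post-baseline values, starting on day 2 (fezolinetant day 2 in the 52-week SAP), for numerator and denominator alike. This matches the by-visit liver windows in 6.10.1.2.
- **12-week SAP, 6.5.2.1:** end the window at the last double-blind dose plus one day, and state that the pre-dose Week 12 draw stays with the double-blind arm.

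The cost is two edited definitions and one table rerun per SAP. No scheduled post-dose liver draw falls on day 1 or on the Week 12 dosing day, so none is lost. An elevation that persists past day 1 is still counted. An unscheduled post-dose draw on the first-dose date could be kept where draw and dose times are recorded.
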